In addition an interim review of blinded or unblinded data by an Interim Analysis Committee may be performed at any time as described in Section 11.6, Interim Analysis.

SUBJECT POPULATION

Subjects in the early AD spectrum, i.e., subjects asymptomatic at risk for Alzheimer's dementia and prodromal AD subjects at time of enrollment in 54861911ALZ2002 study, who have completed their treatment period as defined under the parent protocol in a Phase 1b or Phase 2 clinical study with JNJ-54861911 will be provided the opportunity to participate in this study. If not defined in 54861911ALZ2002 study, completion of the treatment period is defined as having completed all study related procedures of the last visit of the treatment period under the in 54861911ALZ2002 study.

Subjects who have progressed to dementia in the in 54861911ALZ2002 study ($CDR \geq 1$) or who are incapable of providing informed consent will not be enrolled.

In case the subject progresses to a dementia state during the study, the subject may remain in the study, provided that the investigator judges that the potential benefits of treatment for this subject clearly outweigh the known and foreseeable risks and then the assent or consent (as applicable) for continued participation is obtained from a representative determined in accordance with the local law. In cases where a subject has progressed to dementia, treatments indicated for this condition (e.g., memantine or cholinesterase inhibitors) are permitted after notification of the sponsor.

Screening for eligible subjects should be performed as soon as possible, but within 6 weeks following completion of their treatment period in ALZ2002 study until administration of the study drug. A screening phase of up to 12 weeks may be allowed following written approval of the Sponsor.

The inclusion and exclusion criteria for enrolling subjects in this study are described in more detail in Section 4.

DOSAGE AND ADMINISTRATION

Study medication will be provided as JNJ-54861911 tablets, strengths 5-mg, 25-mg and matching placebo, blister packed. All tablets (JNJ-54861911/placebo) are physically identical.

Eligible subjects enrolled in this study will participate in 2 sequential treatment phases/periods as described above, i.e.

- **Double-blind treatment phase:** a 52-week (12 Months) placebo-controlled DB treatment phase. Eligible subjects enrolled in this study will receive either JNJ-54861911 (10-mg or 25-mg q.d.) or placebo (q.d.). Subjects will continue on their current treatment regimen assigned in 54861911ALZ2002 study (placebo, 10-mg or 25-mg q.d. JNJ-54861911). Subjects who received an active dose different from 10-mg or 25-mg JNJ-54861911 under 54861911ALZ2002 study will be receiving the closest dose available in DB treatment phase (e.g., subjects receiving 50 mg in study 54861911ALZ2002 will be assigned to 25 mg JNJ-54861911).
- **Open-label phase:** an open label treatment phase during which subjects who received placebo in DB treatment phase will be randomized with equal chance to one of two JNJ-54861911 dose levels, i.e. 5-mg q.d. JNJ-54861911; or 25-mg q.d. JNJ-54861911. Subjects receiving JNJ-54861911 in DB treatment phase will continue their treatment as open label in the OL phase.

During the entire study (DB and OL treatment phases) subjects will self-administer once daily (q.d.) study drug (JNJ-54861911/placebo) with a glass of non-carbonated water, after completion of breakfast or a light snack, during the morning hours, according to the instructions provided by the investigator. During scheduled visits, subjects will self-administer their study medication on site as described above. On Day 1 study drug administration will be administered following completion of all predose assessment and will not be limited to morning hours.

If a subject realizes before 2:00 PM that he/she forgot to take their daily dose, he/she will be instructed to take the daily dose even if late (before 2:00 PM).

If a subject realizes after 2:00 PM he/she forgot to take his/her daily dose, he/she will be instructed not to take any dose during that day, but resume dosing the following day.

Subjects who are no longer capable of ensuring treatment compliance in the judgment of the investigator (e.g., due to progression to dementia) have to be supported in study drug handling and administration (e.g., care giver or nurse practitioner). In cases where support cannot be provided subjects should be discontinued from treatment and withdrawn from the study.

SAFETY EVALUATIONS

The primary objective of this study is to assess the long-term safety and tolerability of JNJ-54861911 in subjects in the early AD spectrum. As such, regular safety assessments will be performed as listed in the Time and Events Schedule. These safety assessments include but are not limited to: vital signs, ECG, physical and neurological examination, adverse events, safety labs, suicidality risks (Columbia Suicide Severity Rating Scale [C-SSRS]), dermatologic and ophthalmologic examinations and MRI. Protocol amendment 5 was written to include more frequent monitoring of serum chemistry and hematology, guidelines for discontinuation of treatment due to abnormal liver enzymes and guidelines for evaluation and management of such cases.

Specific dermatologic and ophthalmologic examinations have been implemented in this study as potential BACE1- or BACE2-linked toxicities (e.g. melanin deposition changes and retinal abnormalities) have been described in the literature (e.g., BACE1 or BACE2 knock-out mice). With the exception of fur discoloration resulting in progressive lightening of the fur from normal dark brown to paler cream or grey, which was seen in one species only (Tg mice in the 6 month carcinogenicity study), however, these toxicities have not been observed in nonclinical chronic studies with JNJ-54861911.

In addition to the (safety) MRI assessments performed in 54861911ALZ2002 (if applicable), safety MRIs will be collected in this study during both DB and OL treatment phases, as indicated in the Time and Events Schedule, to monitor for amyloid related imaging abnormalities (ARIA)-edema or effusion (E) and ARIA-hemosiderin (H). In case of any safety related changes observed (e.g., ARIA-E or H), additional safety MRIs may be collected at a frequency as recommended by the DRC.

Any changes observed in any of the safety measures performed that are considered not clinically significant or do not have a direct clinical symptomatology as assessed by the investigator, should be closely monitored, with a potential increased safety monitoring frequency as deemed appropriate by the investigator. In addition, these findings will be presented to the DRC, who will make recommendations regarding the safety and continuation of the study as per its charter.

PHARMACOKINETIC EVALUATIONS

Venous blood samples for analysis of JNJ-54861911 will be collected at the time points indicated in the Time and Events Schedule.

CSF samples for analysis of JNJ-54861911 concentrations will be obtained at the time points indicated in the Time and Events Schedule.

COGNITION, FUNCTION AND CLINICAL STATUS

Cognitive evaluations (RBANS, MMSE and CVLT-II) and functional outcome measures (Cognitive Function Index [CFI]) will be applied in this study at different time points as indicated in the Time and Events Schedule to explore the subject's cognitive performance/progression and function over time.

In addition during course of the study the subject's clinical status will be assessed regularly by means of the Clinical Dementia Rating Scale as indicated in the Time and Events Schedule.

BIOMARKER EVALUATIONS

Fluid (CSF and plasma samples) biomarkers samples and imaging biomarker assessments (MRI) will be performed as listed in the Time and Events Schedule to assess the potential and continuous effects of JNJ-54861911 on the pathological and pathophysiological processes of AD. In addition, these biomarker assessments will be performed to assess if potential treatment effects of JNJ-54861911 are consistent with the putative effects of BACE inhibition.

During the course of the study the continuous effects of JNJ-54861911 on the pathophysiological processes of AD will be monitored by the DRC.

All subjects will undergo an MRI in this study at the time points indicated in the Time and Events Schedule for primarily safety reasons. However, potential treatment effects may be assessed with MRI as well.

STATISTICAL METHODS

Sample Size Determination

This study is not powered according to statistical calculations. The number of subjects enrolled will depend on the number of subjects from other JNJ-54861911 studies who are willing to enroll in this study.

Statistical Analysis

Descriptive statistical analyses will be performed for all subjects receiving at least one dose of study drug. Analyses may be prepared separately for DB and OL treatment phases, and may be performed separately for subgroups of subjects according to previous study participation as well as for the combined population of all subjects participating in this study, where appropriate. Summaries may also be presented by baseline CDR global score.

Data Review Committee (DRC)

A DRC will be established to review/monitor the study data on an ongoing basis to ensure the continuing safety of the subjects enrolled in this study. The committee will meet periodically to review interim study data including the biomarker data (fluid [CSF, plasma] and imaging [volumetric MRI]).

After the review, the DRC will make recommendations regarding the safety and continuation of the study. The details will be provided in a separate DRC charter.

The DRC responsibilities, authorities, and procedures will be documented in its charter.

TIME AND EVENTS SCHEDULE

Phase Treatment Period Time Period Study Visits: Day/Week/Month Visit Window	Screening	Double-Blind Treatment Phase							Open-Label Treatment Phase	End-of- Treatment Visit (or phone call) or Early Withdrawal ⁿ	
		Period 1 Day 1 to Week 52 (Month 12)							Period 2		
		0 to 6 weeks	Day 1	Week 8	Week 12	Week 16	Week 24	Week 36	Week 52 (Month 12)ⁿ	>Week 52 (>Month 12)	30 days post last dose
		0	+/- 12 days	+/- 12 days	+/- 12 days	+/- 12 days	+/- 12 days	+/- 12 days	+/- 12 days	+/- 12 days	
Study Procedures											
Screening/Administrative											
Informed consent	X										
Inclusion/exclusion criteria	X										
Medical History and Demographics	X										
Prestudy therapy	X										
Preplanned surgery/procedure(s)	X										
Study Drug Administration											
Randomization								X ^o	See separate Time and Events Schedule Treatment Period 2		
Dispense study drug		X		X		X	X	X ^o			
Self-Administer study drug ^a		X-----X									
Drug accountability		X		X		X	X	X			
Drug return				X		X	X	X			
Safety Assessments											
Physical and Neurological examination		X ^{b,c}						X			
Vital signs		X ^{b,c}				X		X			
Body Weight		X ^{b,c}						X			
12-lead ECG ^d		X ^{c,s}				X ^s		X ^s			
Temperature		X ^{b,c}				X		X			
Dermatologic Examination ^{p,x}		X ^{c,e,f}				X		X			
Ophthalmologic Examination		X ^{c,e,f}				X ^m		X ^m			

Phase	Screening	Double-Blind Treatment Phase							Open-Label Treatment Phase	End-of-Treatment Visit (or phone call) or Early Withdrawal ⁿ
Treatment Period		Period 1							Period 2	
Time Period		Day 1 to Week 52 (Month 12)							>Week 52 (>Month 12)	
Study Visits: Day/Week/Month	0 to 6 weeks	Day 1	Week 8	Week 12	Week 16	Week 24	Week 36	Week 52 (Month 12) ⁿ		30 days post last dose
Visit Window		0	+/- 12 days	+/- 12 days	+/- 12 days	+/- 12 days	+/- 12 days	+/- 12 days	+/- 12 days	+/- 12 days
Study Procedures										
OCT ^{t,x}		X ^{c,e,f}				X		X	See separate Time and Events Schedule Treatment Period 2	
C-SSRS (baseline)		X ^{c,g}								
C-SSRS (since last visit)		X ^{c,g}		X		X	X	X		X
Cognitive & Functional Evaluations ^h										
RBANS		X ^{b or i}				X		X		
MMSE		X ^{b or i}						X		
CVLT-II				X						
CFI		X ^{b or i}				X		X		
Clinical Scales ^h										
CDR		X ^{b or i}						X		
Clinical Laboratory Assessments										
Hematology, Chemistry		X ^{b,c}	X		X	X	X	X		
Urinalysis		X ^{b,c}				X		X		
Pharmacokinetics										
Blood Sample collection		X ^{c,s}				X ^{c,s}		X ^{c,s}		
Fluid Biomarkers										
Blood sample collection		X ^c				X ^c		X ^c		
CSF sample collection ^l		X ^{c,k}						X ^l		
Imaging										
MRI ^{q,x}		X ^{c,t,i}				X		X		
Ongoing Subject Review										
Concomitant therapy	X	X		X		X	X	X	X	X
Adverse events	X	X		X		X	X	X	X	X

TIME AND EVENTS SCHEDULE (OPEN-LABEL TREATMENT PHASE)

Phase	Open-Label Treatment Phase						
Treatment Period	Treatment Period 2						
Time Period	>52 weeks						
Study Visit	Every 2 weeks	Every 4 weeks	Every 8 weeks	Every 12 weeks	Every 24 weeks(*)	Every 48 weeks(*) (#)	Every 96 weeks(*) (#) (¥)
Visit Window	+/- 3 days	+/- 12 days	+/- 12 days	+/- 12 days	+/- 12 days	+/- 12 days	+/- 12 days
Study Procedures							
Drug accountability/Treatment compliance				X			
Drug return (previous visit)				X			
Drug Dispensing				X			
Self-Administer study drug ^a	X-----X						
Physical and Neurological examination						X	
Body Weight						X	
12 Lead ECG				X ^{l,s}	X ^s		
Body Temperature					X		
Supine and standing vital signs (systolic and diastolic blood pressure and pulse)				X			
Clinical safety laboratory assessments – hematology, serum chemistry– under fasted conditions, when feasible	X ^t	X ^u	X ^v	X ^w			
Clinical safety laboratory assessments – urinalysis–under fasted conditions, when feasible					X		
Dermatological Examination ^{p,x}						X	
Ophthalmological Examination ^m						X	
OCT ^{r,x}						X	
C-SSRS (since last visit)				X			
RBANS					X		
MMSE						X	
CFI					X		
CDR						X	
Blood sample collection for plasma JNJ-54861911 concentrations					X ^{c,s}		
Blood sample collection for PD/biomarkers					X ^c		
CSF sample collection (~12 mL) by single lumbar puncture for PK/PD/biomarker assessment. ^j							X ^l
MRI ^{q,x}						X	
Adverse Event and Concomitant Medication				X			

Abbreviations = CDR: Clinical Dementia Rating Scale; CFI: Cognitive Function Index; CSF: cerebrospinal fluid; C-SSRS: Columbia Suicide Severity Rating Scale; CVLT-II: California Verbal Learning Test – Second Edition; DRC: Data Review Committee; ECG: electrocardiogram ; MRI: Magnetic Resonance Imaging; MMSE: Mini Mental State Examination; OCT: Optical Coherence Tomography; PK: pharmacokinetic(s); PD: pharmacodynamics; RBANS: Repeatable Battery for the Assessment of Neuropsychological Status.

TIME AND EVENTS SCHEDULE (FOOTNOTES)

Footnotes

- ^a Subjects will self-administer study drug (once daily) with a glass of water following breakfast or a light snack. Study drug administration will take place during the morning hours. During scheduled visits when ECG or blood samples for JNJ-54861911 concentrations in plasma are to be obtained subjects will self-administer their study medication on site as described above. On Day 1 study drug administration will not be time limited.
- ^b Baseline (predose) only if no (adequate) assessment was obtained under the parent protocol at the last study visit of the treatment phase.
- ^c Must be performed predose.
- ^d At all time points, triplicate ECGs are required, i.e., 3 individual ECG tracings should be obtained as closely as possible in succession, but no more than 2 minutes apart. The full set of triplicates should be completed in less than 4 minutes.
- ^e Only if no adequate assessment was obtained under the parent protocol within 9 months of first dosing in this study.
- ^f May be performed during screening in case of logistical issues.
- ^g C-SSRS baseline: Only to be completed if no C-SSRS assessment was performed under the parent protocol; C-SSRS since last visit: to be completed if the C-SSRS assessment was performed under the parent protocol.
- ^h The RBANS will be completed first followed by the CDR and MMSE if the raters for RBANS and CDR are independent. If the raters for RBANS and CDR are the same, the CDR will be performed first, followed by the RBANS and MMSE.
- ⁱ Only if no adequate assessment was obtained under the parent protocol 6 months prior to first dosing in this study.
- ^j CSF samples (12 mL/sample; baseline and on treatment samples) should be taken at approximately the same time of day (with an allowable window of 3 hours), with the on treatment samples being collected postdose. In Treatment Period 2 (>52 weeks) it is intended to collect if possible on-treatment CSF samples every 96 weeks until study completion. Subjects may opt not to have these punctures being performed. CSF samples collected will be used for biomarker and PK analysis.
- ^k Only if no on-treatment CSF sample was collected under the parent protocol (54861911ALZ2002 study).
- ^l Only during the first 12 week visit of the open-label treatment phase.

- ^m Ophthalmologic examination will be performed only if: 1) if there was an abnormality present at the screening/baseline examination; 2) if the investigator detects new ophthalmological findings or visual symptoms; 3) if OCT reveals new findings. The ophthalmologic examination should be performed by the same ophthalmologist who completed the initial ophthalmologic examination at screening/baseline.
- ⁿ If a subject discontinues study treatment the subject will be asked to complete the Week 52 assessments, including CSF sampling, if not yet obtained earlier. In addition, and at a minimum the subject will be asked to complete the End-of-Treatment Visit (Follow-up visit) as per Time and Events Schedule.
- ^o At Week 52 subjects will be dosed according to treatment allocation assigned to in Treatment Period 1. Randomization to Treatment Period 2 and dispensation of study medication for Treatment Period 2 will only be performed following completion of all week 52 assessments.
- ^p Whenever a skin lesion not previously documented is reported by the study subject or the investigator, in addition to a dermatological exam by the dermatologist, digital images of the lesion will be acquired at the time the lesion is discovered and at follow-up visits with a frequency which is deemed appropriate by the sponsor of the study. Duration of follow-up of newly documented skin lesions or depigmentation might extend beyond the treatment period, as judged adequate by the sponsor to ensure the safety of subjects in this study.
- ^q Additional MRI scans may be collected based on emerging safety data with a frequency as recommended by the DRC.
- ^r At sites where OCT is available.
- ^s 2 to 4 hours postdose.
- ^t Hematology and serum chemistry assessments to be performed every 2 weeks for 12 weeks (from Week 52 to Week 64, inclusive).
- ^u Hematology and serum chemistry assessments to be performed every 4 weeks for 12 weeks (from Week 64 to Week 76, inclusive).
- ^v Hematology and serum chemistry assessments to be performed every 8 weeks for 24 weeks (> Week 76 and ≤ Week 100).
- ^w Hematology and serum chemistry assessments to be performed every 12 weeks after Week 100.
- ^x Assessments can be done not only on the visit date but also within the visit window of +/- 28 days, with a preference to have these procedures performed prior to the scheduled visit.

** In addition to the assessments performed every 12 weeks.*

In addition to the assessments performed every 24 weeks.

¥ In addition to the assessments performed every 48 weeks.

ABBREVIATIONS

A β	amyloid β (beta)
AD	Alzheimer's disease
ALT	alanine aminotransferase
APP	amyloid precursor protein
ARIA-E	Amyloid related imaging abnormality – edema
ARIA-H	Amyloid related imaging abnormality –hemosiderin
AST	aspartate aminotransferase
AUC	area under curve
BA	Bioavailability
BACE	β -secretase
BACE1	β -secretase 1 (also known as beta-site APP cleaving enzyme 1)
BACE2	β -secretase 2 (also known as beta-site APP cleaving enzyme 2)
BACEi	BACE inhibitor
b.i.d.	Twice daily
BQL	below the limit of quantification
C-SSRS	Columbia Suicide Severity Rating Scale
CDR	Clinical Dementia Rating Scale
CDR-SB	Clinical Dementia Rating Scale – Sum of Boxes
CFI	Cognitive Function Index
CI	confidence interval
C _{max}	maximum or “peak” concentration (Cmax) of a drug observed after its administration
CNS	central nervous system
CrCl	creatinine clearance rate
CRF	case report form (paper or electronic as appropriate for this study)
CSF	cerebrospinal fluid
CVLT-II	California Verbal Learning Test – Second Edition
CYP	cytochrome P450
DIAT	Diaminotiazine
DDI	drug-drug interaction
DRC	Data Review Committee
DTP	data transfer plan
ECG	Electrocardiogram
eDC	Electronic Data Capture
FLAIR	Fluid attenuated inversion recovery
GCP	Good Clinical Practice
GLP	Good Laboratory Practice
GSH	Glutathione
HDPE	high-density polyethylene
IC ₅₀	The concentration of a compound that is required for 50% inhibition
ICF	informed consent form
ICH	International Conference on Harmonisation
IEC	Independent Ethics Committee
INR	International normalized ratio
IRB	Institutional Review Board
IWRS	Interactive Web Response System
JRD	Janssen Research and Development
LC-MS/MS	liquid chromatography/mass spectrometry/mass spectrometry
MAD	Multiple ascending dose
MCI	mild cognitive impairment
MedDRA	Medical Dictionary for Regulatory Activities
MMSE	Mini Mental State Examination
MRI	Magnetic resonance imaging
NFT	Neurofibrillary tangles
NOAEL	No observed adverse effect level

pAD	Prodromal Alzheimer's disease
OCT	Optical Coherence Tomography
PD	Pharmacodynamic(s)
PDPH	Post-dural puncture headache
PET	Positron emission tomography
PHFs	paired helical filaments
PK	Pharmacokinetic(s)
PQC	Product Quality Complaint
POM	Proof of mechanism
q.d.	once daily
RBANS	Repeatable Battery for the Assessment of Neuropsychological Status
RBC	Red blood cell
SAD	single ascending dose
sAPP	soluble amyloid precursor protein
SOP	Standard operating procedure
t_{\max}	time to reach the maximum plasma/CSF concentration
WBC	white blood cells

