9. STUDY EVALUATIONS

9.1. Study Procedures

9.1.1. Overview

The Time and Events Schedule summarizes the visits as well as the frequency and timing of assessments applicable to this study. A visit window of +/-12 calendar days will be allowed for all visits, unless otherwise indicated in the Time and Events Schedule. All visits are in principle single day visits however they may be performed over multiple days within the allowed visit window in cases of logistical issues or a subject's preference.

All subjects within the early (predementia) AD spectrum enrolled in this study being subjects asymptomatic at risk for AD and subjects with pAD, will follow the same procedures as listed in this section unless otherwise specifically indicated.

Information regarding handling, shipment, and labeling of biological samples (including safety labs) will be provided in a separate lab manual.

For CSF sampling, local site standard operating procedures (SOPs) may be applied for performing the actual lumbar puncture (not the collection), provided they are at least as restrictive as the criteria defined in this protocol or lab manual.

Separate imaging manuals and charters will be provided, describing the MRI imaging procedures, data acquisition and handling.

Any changes to the lab manual and imaging manuals/charters will not result in a protocol amendment.

In the event of abnormal safety findings during the conduct of the study, additional measurements may be made immediately and subsequently at a frequency considered appropriate by the attending physician.

The time points for individual measures may be changed (with or without affecting the overall frequency of these investigations) prior to and during the study based on newly obtained data (e.g., interim analysis, DRC) to allow for optimal fit to the actual safety or PK/PD profile of the study drug. This modification may result in a change in the overall frequency of the individual measures (e.g., safety measures, blood and CSF samplings) provided the maximal total blood and/or CSF volume collected per subject defined will not be exceeded. Such modifications, where performed only to allow optimal fit to the actual safety, PK/PD profile of the study drug, will not be considered to be an amendment to the protocol.

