9.1.5. End-of-Treatment Visit (Follow Up Visit)

An End-of-Treatment visit (or phone call) for a safety assessment should take place approximately 30 days after the last dose of study drug. This will consist of at least a review of Adverse Events and concomitant medication and C-SSRS assessment (since the last visit). The study is considered completed with the last End-of-Treatment safety assessment for the last subject participating in the study or upon a decision by the sponsor to terminate the study.

Investigators may recontact the subject to obtain long-term follow-up information to determine the subject's safety or survival status (refer to Section 16.2.3, Informed Consent).

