12.3. Procedures

12.3.1. All Adverse Events

All adverse events and special reporting situations, whether serious or non-serious, will be reported from the time a signed and dated ICF is obtained until completion of the subject's last study-related procedure (which may include contact for follow-up of safety). Serious adverse events, including those spontaneously reported to the investigator within 30 days after the last dose of study drug, must be reported using the Serious Adverse Event Form. The sponsor will evaluate any safety information that is spontaneously reported by an investigator beyond the time frame specified in the protocol.

All other events that meet the definition of a serious adverse event will be reported as serious adverse events, regardless of whether they are protocol-specific assessments.

All adverse events, regardless of seriousness, severity, or presumed relationship to study drug, must be recorded using medical terminology in the source document and the CRF. Whenever possible, diagnoses should be given when signs and symptoms are due to a common etiology (e.g., cough, runny nose, sneezing, sore throat, and head congestion should be reported as "upper respiratory infection"). Investigators must record in the CRF their opinion concerning the relationship of the adverse event to study therapy. All measures required for adverse event

management must be recorded in the source document and reported according to sponsor instructions.

The sponsor assumes responsibility for appropriate reporting of adverse events to the regulatory authorities. The sponsor will also report to the investigator (and the head of the investigational institute where required) all serious adverse events that are unlisted (unexpected) and associated with the use of the study drug. The investigator (or sponsor where required) must report these events to the appropriate Independent Ethics Committee (IEC) that approved the protocol unless otherwise required and documented by the IEC.

For all studies with an outpatient phase, including open-label studies, the subject must be provided with a "wallet (study) card" and instructed to carry this card with them for the duration of the study indicating the following:

- Study number
- Statement, in the local language(s), that the subject is participating in a clinical study
- Investigator's name and 24-hour contact telephone number
- Local sponsor's name and 24-hour contact telephone number (for medical staff only)

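### The End-of-Treatment contact may compliantly fall on Day 18 after the last dose, so solicited adverse-event and C-SSRS follow-up can close before the protocol's own 30-day serious-event period ends

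*Protocol*

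**What the plan says.** The End-of-Treatment column of the Time and Events Schedule is headed "30 days post last dose", and its visit window is +/- 12 days. Section 9.1.1 sets the same default: "A visit window of +/-12 calendar days will be allowed for all visits, unless otherwise indicated in the Time and Events Schedule". The schedule gives no narrower or one-sided window for this contact.

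Section 9.1.5 times the contact at "approximately 30 days after the last dose of study drug", allows a phone call, and gives its minimum content as adverse events, concomitant medication and the C-SSRS since the previous visit. Section 10.1 also ties study completion to a safety assessment at about 30 days.

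Section 12.3.1 has all adverse events reported "until completion of the subject's last study-related procedure (which may include contact for follow-up of safety". It then requires serious events to be reported on the serious-event form, "including those spontaneously reported to the investigator within 30 days after the last dose of study drug". The last sentence of that paragraph says the sponsor will evaluate safety information that investigators report spontaneously after the protocol's time frame.

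**The concern.** For an on-treatment visit, a symmetric window costs little. If the visit is early, the next one asks about the interval since then, so nothing is lost. The End-of-Treatment contact has no next visit, so days given up on the early side are not recovered, while a late contact only lengthens observation. A window that suits the other visits is therefore the wrong shape for the last one.

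The primary objective is long-term safety. If the contact is early, solicited collection can end while the 30-day serious-event period in Section 12.3.1 is still running. For the rest of that period, a new serious event reaches the sponsor only if someone volunteers it. New non-serious events and suicidality are not asked about at all. The length of post-dose observation also varies between subjects for scheduling reasons alone.

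**Working it through.** **Inputs**
- Nominal contact: 30 days after the last dose (Time and Events Schedule; Section 9.1.5 says approximately).
- Window: +/- 12 days. In the schedule's window row, Screening is blank, Day 1 is 0, and each of the eight remaining columns has +/- 12 days, the last being End-of-Treatment. Section 9.1.1 gives the same figure as the default, so the reading does not depend on how the table was extracted.
- Serious-event period: 30 days from the last dose (Section 12.3.1).
- Mean half-life after multiple dosing: 14.4 to 18.5 hours (Section 1.1, multiple-ascending-dose study).

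**Permitted range**
- Earliest: 30 − 12 = Day 18. Latest: 30 + 12 = Day 42.
- Ratio of longest to shortest post-dose observation: 42 / 18 = 2.33.

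**Gap against the serious-event period**
- After a Day 18 contact, Days 19 to 30 remain: 30 − 18 = 12 days, or 12 / 30 = 40% of that period.
- This is the extreme edge. A contact on Day 25 leaves 30 − 25 = 5 days, and a contact on or after Day 30 leaves none.

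**Is there a second contact?** The schedule has no later column. Section 9.1.5 permits investigators to recontact subjects about safety or survival but does not require it. No section asks for another contact at Day 30 when the first was early.

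**Is this contact always the last procedure?** No. Subjects who stop treatment early are asked for the Week 52 assessments if not yet done (Section 10.2 and schedule footnote n), and these could come later. Subjects under liver-enzyme follow-up continue on the Attachment 1 schedule. For a subject with neither, this contact closes collection.

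**Drug exposure at Day 18**
- 18 × 24 = 432 hours.
- 432 / 14.4 = 30.0 half-lives; 432 / 18.5 = 23.4 half-lives.
- The drug is essentially eliminated well before the earliest permitted contact.

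**With a window of 0 to +12 days**
- Range: Day 30 to Day 42. Gap before Day 30: 0 days, against up to 12 now.
- Observation ratio: 42 / 30 = 1.4, against 2.33 now.

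**The case against.** The strongest reply is that nothing here conflicts. Sections 3.1, 9.1.5 and 10.1 all say approximately 30 days, and the window defines what approximately means. The only unqualified 30-day figure belongs to serious events. It runs from the last dose, so an early contact does not shorten it. For other events the stop is a procedure, not a day. This stands: the timing is loosely fixed, and the protocol does not contradict itself. It does not explain why the only contact with nothing after it should be allowed 12 days early. The protocol already departs from the default where it sees a reason: +/- 3 days for the two-weekly laboratory visits and +/- 28 days for dermatology, MRI and OCT.

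A reader might infer more than the documents support:
- **That only spontaneously reported serious events are captured after an early contact.** Section 12.3.1 has the sponsor evaluate any later spontaneous safety information, and Sections 9.2 and 12.3.2 continue follow-up of persisting clinically significant abnormalities and unresolved serious events.
- **That special-interest events in this span are missed.** Section 12.3.4 requires all initial reports within 24 hours even when non-serious. What an early contact removes is the scheduled question that would prompt them.
- **That subjects who stop because of an event are the ones who depend on this contact.** Everyone who ends treatment is due it. Those who stop for an event tend to have more follow-up elsewhere: liver stops are serious events with continued blood sampling (Attachment 1), and Week 52 assessments are requested.
- **That the placebo comparison is biased.** Subjects who complete the double-blind phase pass directly into open-label treatment at Week 52, so the contact bears on that comparison only for early leavers. Section 11.5 limits the adverse-event summaries to onset or worsening in the treatment phase, so on that wording a new event on Days 19 to 30 would not enter them.

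It is also fair to say that the documents name no delayed or withdrawal risk specific to those days.

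**Conclusion.** The point holds as a minor one. The protocol allows its only scheduled post-treatment safety review up to 12 days before its own 30-day serious-event period ends, and it requires nothing to cover the remainder. What is lost is solicitation: serious events in the remaining days rest on spontaneous reporting, and new non-serious events and C-SSRS are not asked about.

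The size is at most 12 days per subject, at the edge of the window, and zero for anyone contacted on Day 30 or later. How many subjects would be contacted early cannot be known from the protocol. The yield from those days is probably small, because the drug is essentially gone by Day 18 and the planned adverse-event summaries would change little, if at all.

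The conclusion assumes a subject with no ongoing follow-up and no later study assessment, so that this contact is the last procedure. It also assumes that sites use the early side of the window as written.

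**What to change.** Change the End-of-Treatment window in the Time and Events Schedule from +/- 12 days to 0 to +12 days, and state in Section 9.1.5 that the contact asks about events through at least Day 30 after the last dose. Section 9.1.1 already lets the schedule override the default, so it needs no edit. This aligns the contact with the serious-event period in Section 12.3.1.

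The cost is one schedule cell and one sentence, with no additional contact. Sites lose some flexibility: permitted days fall from 25 (Day 18 to Day 42 inclusive, 42 − 18 + 1) to 13 (Day 30 to Day 42, 42 − 30 + 1). As the contact may be a phone call, that should be manageable. Some variation in follow-up length remains, from 30 to 42 days, but all of it lies beyond the 30-day period.
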